5.0 REQUIRED EVALUATIONS, STUDY INTERVENTION, AND OBSERVATIONS

All studies in MIDAS will be performed within 30 days of each other. All study participants' medical history will be ascertained and will include all pertinent medical history including, but not limited to, transfusion history, menstrual history, history of endocrinopathies and cardiac disease, medications used including chelation therapy, etc.

5.1 Study Evaluations

Table 2: List of study tests for the MIDAS study.

- | |
|--|
| A. Pregnancy test prior to undergoing MRI examination (for female research participants, including both healthy volunteer and patients, of child-bearing potential only) |
| B. Complete blood count (CBC), Serum ferritin, transferrin saturation, total iron binding capacity, and an extra aliquot of blood for storage ¹ |
| C. Activated partial thromboplastin time (aPTT), prothrombin time (PT), fibrinogen, platelet function analyzer (PFA-100) ² |
| D. Liver biopsy with determination of liver iron concentration and histology ³ |

E. 1.5T and 3T MRI exams of the liver

¹ *An extra aliquot of blood (5cc) will be drawn and stored for future research*

² *Pre-liver biopsy lab work, performed within 48 h of procedure.*

³ *Performed within 30 days of the MRI tests and only in research participants who have a clinical need for liver biopsy as determined by the treating clinician.*

Currently, all iron-overloaded research patients undergo annual R2*-GRE exams (or more frequently if clinically indicated) for clinical monitoring. All iron-overloaded patients will be approached to participate in MIDAS at the time of their regular clinic visit.

All study participants will undergo a 1.5T R2*-GRE and 1.5T R2*-UTE study to evaluate their clinical need for a liver biopsy (Figure 3) In most cases, MRI examination will precede the liver biopsy. In some cases, however, due to occasional clinical urgency in obtaining the liver biopsy study, the liver biopsy will be done prior to MRI exams. In these cases, 1.5T R2*-GRE and 1.5T R2*-UTE MRIs will be done within 30 days following the liver biopsy. In addition, a 3T MRI exams consisting of a R2*-GRE and R2*-UTE will be performed.

If an exam based on a 1.5T R2*-GRE measurement that was analyzed using clinical criteria as established in the AIM09 clinical practice protocol fails according to established criteria (failed or non-converging fit precision in more than 10% of the voxel prescribed in the ROI), a liver biopsy is clinically indicated and will be performed (if recommended by the treating clinician) within 30 days of the MRI exam. In other words, in this case, the current R2*-GRE method fails to provide a predicted HIC value because not enough pixels in the selected ROI capture the MR signal decay. In our experience, the insufficient fit corresponds to increased concentrations of iron in the hepatic tissue, and the threshold at which failed fits are seen in individual pixels begins at about 500 Hz and accentuates above 900 Hz, which corresponds to an HIC of ~ 15 and 25 mgFe/g, respectively.

Healthy volunteers will undergo R2*-UTE and R2*-GRE studies at both, 1.5 and 3T MRI field strengths. No blood work or liver biopsy will be performed on healthy volunteers.

The result of the liver R2*MRI will be shared with the participants' primary clinician and the decision to pursue a liver biopsy will be made by the treating primary clinician. If the participant's primary clinician is from an outside institution (such as in the case of the adult participants), the MIDAS study staff will contact the primary treating clinician and inform him of the MRI results, and a copy of the report will also be mailed or faxed to his office. The primary clinician will review the MRI results and will communicate back with the MIDAS investigators to inform if a liver biopsy is warranted or not. If a liver biopsy is indeed indicated and requested by the treating clinician, an appointment will be scheduled to perform the liver biopsy. Biopsies needed for subjects 26 years of age and older will occur at an adult facility (Regional One Health or other adult hospital), patients 25 or younger will have their liver biopsies performed at St. Jude.

[figure not shown]

Figure 3: Flow diagram for the screening and testing of subjects in the MIDAS study.
Notes: & if participant requires general sedation for MRI, 3T R2*-GRE and R2*-UTE MRIs will not be performed; # participant may still receive a liver biopsy upon treating clinician's discretion. In most cases, MRI examination will precede the liver biopsy. In some cases, however, due to occasional clinical urgency in obtaining the liver biopsy study, the liver biopsy

will be done prior to MRI exams. In these cases, 1.5T R2*-GRE and 1.5T R2*-UTE MRIs will be done within 30 days following the liver biopsy.

Sample Storage

To enhance the scope of research that can be conducted within the MIDAS study, we will establish a biologic repository consisting of stored blood (DNA, serum phase) from all MIDAS participants. An extra aliquot of blood (5cc) will be obtained and consent provided for the collection, storage and future utilization for research investigations through a currently approved tissue bank protocol. Potential investigations utilizing the biologic specimens include, but are not limited to, more extensive laboratory analyses of biomarkers of iron metabolism and iron overload-predisposing genetic mutations. Accession of samples for future research will require approval of the planned research by the Tissue Resource Committee and the Institutional Review Board. In addition to the protocol-specific testing of specimens, study participants will be offered the option of allowing any leftover serum, or blood cells to be saved or shared for future analyses. Leftover serum or blood cells from subjects enrolled in the MIDAS protocol will be de-identified prior to storage or any future testing and/or sharing and will be kept indefinitely in Tissue Resources at St. Jude.

5.2 Off-Study Evaluations

Subjects will be considered off-study 10 days after all study tests have been completed. No off-study evaluations will be required.

5.3 Long-Term Follow-up Evaluations

Not applicable.

5.4 Staff Training and Integrity of Study Procedures

Radiological staff will be trained to appropriately draw ROIs on R2*MRI maps or T2*MRI source images. The software developed by St. Jude physicists is very interactive and easy to use. Staff will undergo training to perform this test and quality control assessment of their ROI measurements will be performed on a regular basis.

6.0 CRITERIA FOR REMOVAL FROM PROTOCOL AND OFF-STUDY CRITERIA

Subjects will be removed from the study if intolerance to performing the MRI study precludes its completion. Subjects will also be removed from protocol at the subject and/or parents request.

7.0 SAFETY AND ADVERSE EVENT REPORTING REQUIREMENTS

MRI does not involve radiation, therefore there are no risks associated with radiation injury. As reiterated in a recent report,⁶⁶ non-sedate MRI generally is considered a minimal risk study. Female participants (both patients with iron overload and healthy volunteers) of child bearing potential, however will be required a negative pregnancy test prior to undergoing an MRI exam. Study participants may need to be sedated for the MRI exam, which may expose the subjects to

the risks involved with anesthetics and airway complication. In the event that a research participant requires sedation with general anesthesia, only the 1.5T MRIs will be performed. The 3T MRI scan will be entirely omitted due to the risks of an additional sedation for a research study.

R2*MRI is done on a regular basis and the additional R2*UTE exams that will be offered in MIDAS will be an additional 30 minutes of MRI table time at 1.5T. The total time of the additional 3T measurement is about 1 hour table time (including scout imaging and the R2*-GRE). Subjects may experience anxiety and claustrophobia during MRI exams, however. If this occurs, the study will be temporarily interrupted, and the subject will be given instructions on how to best tolerate the exam and offered to watch movie or listen to music to help with the relaxation process during the test. In addition, St. Jude Child Life Services have worked very closely with our pediatric subjects and have helped by offering distraction techniques which have improved the tolerance to not only MRI tests, but many other imaging studies. If even after all these measures the study subject is still not able to tolerate the MRI study, the study will be interrupted.

Liver biopsy is an invasive procedure that may involve risks such as pain, bleeding, and infection. Liver biopsy data will be collected only in research participants who are already undergoing a liver biopsy for clinical indications, as recommended by the treating clinician. Liver biopsy is not a condition for participation in the MIDAS study, and therefore HIC quantitation by liver biopsy will be obtained *only* for subjects with a clinical indication for this test. Research participants can undergo the MRI or a liver biopsy initially, and in research participants in whom the noninvasive method (with MRI) is done first and failed to provide a HIC measurement and it is necessary to obtain this information for proper clinical management, a liver biopsy might be recommended by the treating clinician.

7.1 Reporting Serious Adverse Events

A serious adverse event (SAE) is defined as any untoward medical occurrence that at any dose:

- Results in death.
- Is life-threatening (i.e., an event in which the subject was at risk of death at the time of the event; it does not refer to an event which hypothetically might have caused death if it were more severe).
- Requires inpatient hospitalization or prolongation of existing hospitalization.
- Results in persistent or significant disability/incapacity.
- Results in a congenital anomaly birth defect.
- In the opinion of the investigator, important medical events that may not be immediately life-threatening or result in death or hospitalization but may jeopardize the subject or may require intervention to prevent one of the other outcomes listed in the definition above and

may be considered serious. Examples of such events are intensive treatment in an emergency room or at home for allergic bronchospasm; blood dyscrasias or convulsions that do not result in hospitalization; or development of drug dependency or drug abuse.

Fatal or Life-Threatening Adverse Events

A fatal adverse event will precipitate the interruption of the study. Permanent closure of the study will be evaluated by the SJCRH IRB.

7.2 IRB Notification by Investigator

In addition to the continuing review reports to the IRB, the Principal Investigator is responsible for reporting all serious or unexpected adverse events that impact the safety of or risk to the study subjects. Unexpected death will be reported to the IRB office immediately. Serious, unexpected events are to be reported within 48 hours, and all others within 10 working days.

7.3 Recording Adverse Events and Serious Adverse Events

Adverse events will be recorded by study investigators in the adverse events form and a copy will be kept in the study file. Participants will remain on study for 10 days following the last study procedure. This will allow for capture of information in the event that a procedure-related adverse event occurs. All adverse events will be documented in the study database. In the event that a subject has an unresolved event at the time he/she is taken off study, for example, infection, he/she will still be taken off-study and the subject will be followed by the attending physician until resolution of the event. Subjects will be assessed for AE's through communication with their respective attending physicians and chart review.

This study will utilize the CTCAE Version 4.0 for toxicity and performance reporting. A copy of the CTCAE version 4.0 can be downloaded from the CTEP home page (<http://ctep.info.nih.gov>). Additionally, the toxicities are to be reported on the appropriate data collection forms.

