7.4 Definitions

7.4.1 Definitions of Adverse Events

The following definitions have been adapted from the 2010 FDA reporting regulations and International Conference on Harmonisation (ICH) guidelines for use in this study:

- i. Adverse Event (AE): An adverse event (AE) is defined as any reaction, side effect, or untoward medical event that occurs during the course of the clinical trial associated with the use of a drug in humans, whether or not the event is considered related to the treatment or clinically significant. For this study, AEs will include events reported by the patient, as well as clinically significant abnormal findings on physical examination or laboratory evaluation. A new illness, symptom, sign or clinically significant laboratory abnormality or worsening of a pre-existing condition or abnormality is considered an AE.

- ii. Suspected Adverse Reaction: Suspected adverse reaction means any adverse event for which there is a *reasonable possibility* that the drug caused the adverse event. For the purposes of IND safety reporting, ‘reasonable possibility’ means there is evidence to suggest a causal relationship between the drug and the adverse event. A suspected adverse reaction implies a lesser degree of certainty about causality than adverse reaction, which means any adverse event caused by a drug. For this study, a suspected adverse reaction will be any event reported by the patient, as well as clinically significant abnormal findings on physical examination or laboratory evaluation that are thought to be related to the MRI exam or liver biopsy.

- iii. Expected adverse event: Several complications are expected to happen in subjects with hematologic conditions (such as hemolytic anemia, painful crisis, etc.) MIDAS expected adverse events are listed in Table 3 and 4.

- v. Unexpected adverse event or unexpected suspected adverse reaction: A MIDAS unexpected AE or unexpected suspected adverse reaction is any AE or SAR that is not a MIDAS expected AE or SAR (listed in Table 3) or not listed at the specificity or severity that has been observed.

Table 3. List of MIDAS expected and potentially serious adverse events in all subjects.

Hematologic Disease Symptoms and Associated Conditions		
Abnormal TCD velocities	Hand-foot syndrome/dactylitis	
Acute chest syndrome	Hematuria	Pain, sternal or rib
Albuminuria	Hemiplegia	Priapism
Amenorrhea	Hemolysis	Proteinuria
Anemia (severe)	Hemorrhagic Stroke	
Aplastic crisis	Hepatic sequestration	Pneumonia

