10.0 OBTAINING INFORMED CONSENT

The informed consent will be obtained by one of the study investigators or his designee in the presence of at least one witness. Subjects identified as eligible for the study will be invited to participate. Although subjects may be recruited from the Adult Program or St. Jude Affiliates, *all participants will be consented in one of the St. Jude Hospital Outpatient Clinics*. A translator will be provided if necessary. The subject and a legal guardian will be introduced to the study. Objectives and procedures required during the study will be discussed with the family and subject, while reading the informed consent. Subjects older than 18 years-old will sign their own informed consent statement. The legal guardian will sign the informed consent if the subject is a minor. Verbal assent will be obtained from subjects 7 to 14 years of age and written assent from subjects 14 to 17 years old.

In addition, during the development of the R2*-UTE technique, healthy volunteers will be needed to implement and test the new R2*-UTE technique. Healthy volunteers will be recruited among St. Jude employees and will also sign an informed consent for MIDAS, and will have their MRI result data added to the study database. Both R2*-GRE and R2*-UTE using both 1.5T and 3.0T MRI field strength testing will be performed in volunteers in order to proper test and implement the technique in both MRI field strengths.

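### After participants leave the site, adverse-event ascertainment is passive: no participant contact is scheduled in the 10-day window, and the named route does not fit healthy volunteers

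*Combined protocol and SAP*

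**What the plan says.** Section 7.3 gives the method: "Subjects will be assessed for AE's through communication with their respective attending physicians and chart review". The same section sets the observation window, "Participants will remain on study for 10 days following the last study procedure", and its purpose: "This will allow for capture of information in the event that a procedure-related adverse event occurs". Study investigators record events on an adverse-event form.

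Section 5.2 adds "No off-study evaluations will be required". Appendix I has two columns, Screening and Visit 2, and the last item in it is the biopsy. No call, visit, diary or questionnaire appears after that.

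Section 7.4.1 defines what counts: "For this study, AEs will include events reported by the patient, as well as clinically significant abnormal findings on physical examination or laboratory evaluation". Its definition of a suspected adverse reaction likewise includes patient-reported events thought to be related to the MRI or the biopsy.

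On who is covered, section 10.0 says "Healthy volunteers will be recruited among St. Jude employees and will also sign an informed consent for MIDAS". Section 5.1 gives volunteers MRI at both field strengths, with no blood work and no biopsy. For patients, section 5.1 says "Biopsies needed for subjects 26 years of age and older will occur at an adult facility", and it notes that adult participants may have a primary clinician at an outside institution.

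**The concern.** The 10-day period exists to catch procedure-related events, and the definitions make the participant's own report a source of such events. The stated method, however, goes to the physician and the chart and does not ask the participant. Two gaps follow.

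First, healthy volunteers are recruited as employees. The documents describe neither an attending physician nor a clinical chart for them, so the stated method has nothing to work on once they have left.

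Second, a biopsied patient is sent home after observation. A later event reaches the study only if the patient tells a physician with whom the study communicates, or receives care that enters a chart the study reviews. Biopsy at another hospital and outside primary clinicians make that chain longer.

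What is at stake is the completeness of the safety record. Section 4.3 uses the earlier MRIRON record to describe biopsy risk, and the MIDAS record could be used in the same way later.

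**Working it through.** The plan states no ascertainment rate, so there is no figure to reproduce. The check sets the sections side by side, then asks what can and cannot be counted.

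**Step 1: which periods have a route**

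| Period or group | Route in the documents |
|---|---|
| During MRI | Staff handle anxiety or intolerance directly (section 7.0) |
| Biopsy to discharge | Observation with vital signs and hematocrit; admission for hemorrhage or significant pain (section 4.3) |
| Patients, discharge to day 10 | Attending physician and chart review (section 7.3); no participant contact |
| Volunteers, scan to day 10 | Same sentence in 7.3, but no attending physician or chart is described for them; some return for repeat scans (section 4.1) |

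The gap lies in the last two rows.

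**Step 2: which events are at issue**

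Section 7.4.2 keeps Grade 1 events out of the database, so the mildest symptoms would not be recorded however they were ascertained. Grade 2 events are recordable. By the grading text, they may need only minimal or noninvasive intervention while limiting daily activities, so a patient could manage one at home. Events severe enough for hospital care should be found by the stated route. The exposed events are those of Grade 2 or higher that are managed at home, or treated elsewhere, without the physician being told.

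**Step 3: what can be counted**

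- Volunteers: about 35, with about 200 patients (section 9.1). Share = 35 / (200 + 35) = 14.9%. This is a share of participants, not of events.
- Biopsies: 41 planned (section 9.1). Section 4.3 reports overnight observation for pain in 7 of 50 MRIRON biopsies; 7/50 = 14%. Applied here, 41 × 0.14 = 5.7. These are in-hospital events that a chart would show, so they do not measure the loss.

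**Step 4: what cannot be counted**

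The documents give neither a rate of at-home events after biopsy nor the fraction that the passive route would capture. As an assumption only, let p be the at-home event rate per biopsy and s the fraction captured. Then expected recorded events = 41 × p × s, and the chance of recording at least one = 1 − (1 − p × s)^41. For p = 5% and s = 50%, the first is 41 × 0.05 × 0.50 = 1.03 and the second is 1 − 0.975^41 = 0.646.

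| Assumed p | s = 100% | s = 75% | s = 50% | s = 25% |
|---|---|---|---|---|
| 2% | 0.82; 56% | 0.61; 46% | 0.41; 34% | 0.21; 19% |
| 5% | 2.05; 88% | 1.54; 79% | 1.03; 65% | 0.51; 40% |
| 10% | 4.10; 99% | 3.08; 96% | 2.05; 88% | 1.03; 65% |

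(Expected recorded events; chance of at least one.)

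With 41 biopsies the absolute numbers are small under all of these assumptions. The table shows only that the record depends on a capture fraction that the plan neither states nor controls.

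**The case against.** The case on the other side has real force.

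- Section 7.3 states a method without excluding others. A reader might infer that ascertainment in volunteers is nil, or that events after discharge are largely invisible. The documents do not support either. They are silent on whether volunteers have a chart or physician, nothing prevents a volunteer from reporting an event, and a subgroup returns for further scans. This part of the objection stands.
- A patient who tells the attending physician has reported the event, and 7.3 provides for communication with that physician. Section 5.1 shows staff already in two-way contact with outside clinicians. So 7.3 and 7.4.1 do not flatly contradict each other. However, the contact described in 5.1 concerns MRI results and the biopsy decision, and no schedule or responsibility for asking about adverse events is given.
- Biopsy is done only on clinical indication, so relying on the treating clinician is reasonable. Section 7.0 calls non-sedated MRI generally minimal risk. Both points lower the expected yield. They do not supply a route for volunteers, and sections 7.3 and 7.4.1 still bring procedure-related events into the study's scope.
- A reader might infer that the study will issue an unsupported safety claim, or that the reporting deadlines in 7.2 will fail. The plan has no safety objective and no planned safety analysis. The 48-hour deadline covers serious, unexpected events, and by the criteria in 7.1 most of these would be medically attended. Neither inference should be drawn.

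**Conclusion.** The point holds in a limited form. Attending physicians and charts are the only named route, nothing is scheduled with the participant in the 10-day window, and the route does not fit about 35 MRI-only volunteers (14.9% of about 235 participants). Among patients, Grade 2 or higher events managed at home or elsewhere without the physician being told can be missed, although patient-reported events count by definition.

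Neither the 14.9% nor the 5.7 expected overnight stays estimates events lost, and the number missed cannot be derived from the documents. The conclusion rests on reading the silence in 5.2, 7.3 and Appendix I as meaning that no participant contact is planned. If an operating procedure outside these documents provides one, it should be cited in 7.3. The effect is on completeness of the safety data alone; the primary correlation analysis and the 41-biopsy target are untouched. This is a cheap improvement, not a flaw that threatens the study.

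**What to change.** Amend section 7.3 along these lines:

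> Adverse events will be assessed (a) by asking every participant at the end of each study MRI; (b) by one brief scripted contact at the end of the 10-day window with each biopsied participant (or guardian), each patient sedated for a study MRI, and each healthy volunteer; and (c) for patients, by communication with the attending physician and chart review.

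Add the end-of-window contact to Appendix I as a row. Sedated patients are included because section 7.0 links sedation to anesthetic and airway risk, and some of them will be among the roughly 200 − 41 = 159 patients without a study biopsy.

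The cost is 41 + 35 = 76 short contacts, plus one for each sedated patient without a biopsy (a number the documents do not give), over about 4 years by existing study staff. The question at the end of the scan adds little to a visit already taking place. No sample size, endpoint or analysis changes.

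In the same amendment, reconcile 7.3, which has all adverse events documented in the database, with 7.4.2, which leaves Grade 1 events out, so that the script asks for what will be recorded.
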